When discharge from NUMC is imminent, [name], NP, the Director of the NUMC Heart Failure Clinic, will review the study with the patients and consent will be obtained if the subject is willing to be part of the study. The study will be described in detail, and patients will be assured of confidentiality. Once patients give permission (in writing) to discuss the study, the clinic nurse will personally introduce the patient to the bi-lingual research nurse (TBA), and reiterate their willingness to participate, the formal consent process will occur. The research nurse will discuss the study with the patient, including a discussion of the overall goals of the study, the study design, the study time frame (3 months), and the randomization procedures. The nurse will also gather basic information regarding inclusion and exclusion criteria (ex., NYHA class). If the patient meets the inclusion criteria, the nurse will read the consent form aloud, in the patient's primary language, which contains information regarding confidentiality of protected health information, the de-identification of data, risks and benefits of study participation and a description of compensation for participation. The nurse will explain that the information collected regarding daily health could be shared with the patient's physician when necessary, but is completely de-identified for research purposes and will not be shared with anyone else at any time. The consent form will also underscore that the patient can withdraw from the study at any time with no consequences. The nurse will also make sure that the patient understands that he/she will be randomized to either the telehealth self management (TSM) intervention or a control group which is standard of care. However, the nurse will explain to the patient that enrollment for the telehealth arm of the study has ended and he/she will be enrolled in the standard of care arm. If the patient agrees to participate, she/he will be asked to sign an informed consent form. The informed consent will comply with all HIPAA and IRB requirements. We will conduct a block randomization technique to ensure equivalency of gender and Heart Class 3 patients across the two groups. Patients will be randomized by the Feinstein

Biostatistics Unit, as utilized in our previous studies. CAB members and patients who participate in the focus groups will be compensated \$50. Patients in both arms of the RCT will receive \$100 for participation.

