2a. Measures of Inpatient Utilization. Inpatient utilization will be measured in three ways, including: 2a.1) whether an individual subject had at least one inpatient hospitalization over the 3 month period; 2a.2) the number of hospitalizations experienced by an individual subject over the 3 month period; and 2a.3) cumulative length of stay (LOS) (inpatient days) experienced by an individual subject over the 3 month period (i.e., for multiple hospitalizations, the sum of all LOS's will be computed as the cumulative LOS). Cumulative LOS will be analyzed in two ways: intention to treat (ITT) analysis, and for only those hospitalized. The ITT analysis will include all patients, regardless of hospitalization history, to address the bigger public health issue: does TSM have an impact on LOS overall? A secondary analysis will look at LOS only for those who experienced a hospitalization. Finally, after ITT analysis, secondary analyses will include covariate adjustments for possible confounders.

Statistical Methods: Inpatient Utilization. For outcome 2a.1, the proportions of patients in each group who were hospitalized will be compared using the standard Chi-square or Fisher's exact test. Associated 95% confidence intervals for these proportions and their differences will be computed using exact methods. For outcome 2a.2, the number of hospitalizations will be compared using Poisson regression (SAS PROC GENMOD). It is likely that, due to excess zeros (i.e., zero inflation), methods for overdispersed Poisson will be required. Another approach for both outcomes 2a.2 and 2a.3 will be to use Lachenbruch's two stage procedure for zero-inflated data.30 For these primary ITT analyses, no adjustments will be made for any covariates.

Sample size considerations: We expect to enroll 52 patients in the TSM group which will yield the necessary statistical power.

2b. Measures of ER Utilization, defined as: 2b.1) whether or not an individual subject had at least one ER visit over the 3 month period; and 2b.2) the number of ER visits experienced by an individual subject over the 3 month period. Covariate adjustments will be made for potential confounders.

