Statistical Methods: ER *Utilization*: The statistical methods for analyzing ER utilization outcomes will be similar to those presented for inpatient utilization. Specifically, for outcome 2b.1, the proportions of patients in each group who utilized the ER will be compared using the standard Chi-square or Fisher's exact test. Associated 95% confidence intervals for these proportions and their differences will be computed using exact methods. For outcome 2b.2, (overdispersed) Poisson regression will be used. For outcome 2b.2, Lachenbruch's two stage procedure for zero-inflated data will also be considered.²⁵

Sample Size Considerations. The sample size and power considerations identified for outcomes 2a.1 and 2a.2 are virtually identical for ER utilization.

2c. Quality of Life assessment: We will use the Minnesota Living with Heart Failure Questionnaire²⁷ (Appendix 4) to assess patient QoL (QoL). While HF will continue to impact the lives of these patients, it is reasonable to believe that proper disease management via telehealth will improve QoL due to earlier exacerbation detection and lowered hospital utilization. We will compare questionnaire results between patients receiving TSM and usual care patients. Measures of QoL are defined as the 3 month QoL score minus the 1 month QOL score, where a positive score indicates a worsening of QoL .

Statistical Methods. A two-sample z-test will be used to compare changes in QoL between groups.

Sample size and power considerations. we expect to enroll 52 patients in each group, a 2-sample z test (80% power) to detect an effect size of 0.39 or greater, which is considered "small" to "medium".²⁸

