## A Randomized, Controlled Trial Comparing Telehealth Self-Management to Heart Failure Clinic Outpatient Management in Black and Hispanic Disparity Patients Living with Heart Failure

[name], [name], MA, [name], [name], [name], [name], NP, [name], MS, [name], [name], [name], LMSW, [name], MSN, [name], and [name], MPH

The health system's Biostatistics Unit created a randomization schedule for patient assignment, to randomize patients to either TSM or COM using permuted block randomization, with stratification by heart class, to ensure equal representation of heart class across the two groups. The primary analysis of this randomized clinical trial was based on intention to treat (ITT) principle, which included all subjects randomized. Descriptive statistics are presented as means, standard deviations, medians, ranges and frequency/percentages.

Inpatient utilization was defined in three ways, including: 1) whether an individual patient had at least one inpatient hospitalization over the 90 day period; 2) the number of hospitalizations experienced by an individual patient over the 90 day period; and 3) the cumulative length of stay (LOS) (inpatient days) experienced by an individual patient

over the 90 day period (i.e., for multiple hospitalizations, the sum of all LOS's was computed as the cumulative LOS).

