ED utilization was defined as whether or not an individual patient had at least one ED visit over the 90-day period. Binary outcomes for ED visits and hospitalizations were analyzed using the standard Chi-square or Fisher's exact test. Associated 95% confidence intervals for these proportions and their differences were computed using exact methods. The number of ED visits as well as hospitalizations within each group were separately compared using Poisson regression (SAS PROC GENMOD). Due to excess zeros (i.e., zero inflation), methods for over dispersed Poisson were required for both ED visits and hospitalizations. Cumulative LOS (inpatient days) was analyzed using a negative binomial regression. HF-related hospitalizations, ED visits, and LOS were analyzed in the same fashion described above, as were cardiovascular related outcomes. Reasons for ED visits as well as hospitalizations were classified as: HF alone (yes/no), cardiovascular related alone (yes/no), or both by the clinical team.

Repeated measures analysis of variance (RMANOVA) with a mixed models approach was used to compare changes at enrollment and at 90 days between groups. New York Heart Association (NYHA) class, PHQ-4, MLHFQ Physical and Emotional subscales were also analyzed using RMANOVA. The subscales of Anxiety and Depression, as measured by the PHQ-4, were dichotomized to presence or absence and Generalized Estimating Equations (GEE) were used to analyze these binary data. Days at home was

calculated as a proportion of days spent out of hospital during the 90 day period. The two groups were compared using the Mann-Whitney test.

Subgroup analyses included: patients hospitalized, heart class (2 vs. 3), and patients not receiving home care (prevalent in disparity populations). For the TSM group only, adherence was calculated, with low adherence defined as less than 10 vital signs uploads over the 90 day period.

Sample size and power calculations were based on previous literature and preliminary data from a non-disparity randomized RCT TSM study. We hypothesized that 75% of patients in the COM group would be hospitalized at least once during the study period and that TSM would reduce that rate to 50% (a relative reduction of 50%). The calculation was based on a chi-square test (alpha=0.05, two-tailed) with an n=52 patients per group. All analyses were performed using SAS 9.4 (SAS Institute Inc., Cary, NC).

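### The QoL analysis is not stated to condition on the enrolment score, which may cost useful power; as a minor point, the primary hospitalisation and ER tests ignore the heart-class stratum used in randomisation

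*Protocol*

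**What the plan says.** **QoL.** Protocol section 2c defines the measure as month 3 minus month 1 and states: "A two-sample z-test will be used to compare changes in QoL between groups". It then gives 52 per group, 80% power and an effect size of 0.39. The SAP instead describes a repeated-measures analysis with a mixed model, using enrolment and 90 days. It mentions neither an enrolment covariate nor a constraint on enrolment means.

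The reference time point differs between places:
- Enrolment: the Protocol text on TSM Intervention Component 2, and the SAP.
- Month 1: Protocol Table 1, the Standard of care (Control Group) text, and section 2c.

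**Randomisation.** The SAP randomises "using permuted block randomization, with stratification by heart class". Protocol, Recruitment Procedures, says: "We will conduct a block randomization technique to ensure equivalency of gender and Heart Class 3 patients across the two groups".

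**Hospitalisation and ER.** For the inpatient outcomes (Protocol 2a): "For these primary ITT analyses, no adjustments will be made for any covariates". For ER, the Protocol says the proportions of patients "who utilized the ER will be compared using the standard Chi-square" or Fisher's test, and the SAP agrees: "Binary outcomes for ED visits and hospitalizations were analyzed using the standard Chi-square". Protocol 2b also says "Covariate adjustments will be made for potential confounders", without giving a model or saying whether that analysis is primary.

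**Adjusted analyses already planned.** Protocol 2a and the section Secondary Analyses: Adjusting for Confounders provide secondary analyses with gender and heart class among the covariates. They name models for hospitalisation yes/no, number of hospitalisations and length of stay. No model is named for ER or QoL.

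**The concern.** A change score gives the enrolment value a fixed weight of one. Unless the two scores are very highly correlated, that carries more noise than regressing the month 3 score on the enrolment score. QoL is part of the trial hypothesis, although Table 1 labels only ER use and hospitalisations as primary. Power lost here could be recovered without extra patients.

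For the yes/no outcomes, stratified randomisation removes chance imbalance in heart class between arms, but an unstratified test still counts between-class variation as noise. If class predicts hospitalisation, the test is somewhat conservative.

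The reference time point matters before any model is chosen. If month 1 is a visit after randomisation, month 3 minus month 1 subtracts whatever benefit TSM has already produced.

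**Working it through.** **1. The Protocol's own QoL figure.** Inputs from section 2c: 52 per arm, 80% power, effect 0.39. Two-sided 5% is taken from the SAP's hospitalisation calculation. Detectable effect for a two-sample z-test = (1.960 + 0.842) × √(2/52) = 0.549, so 0.39 is not reproduced. It matches the one-sample formula with 52 (2.802/√52 = 0.389), or 104 per arm. That is a separate matter, but it is why power at 0.39 starts low.

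**2. QoL: change score against ANCOVA.** Assume equal SDs σ at both times and correlation ρ.
- Variance of change: 2σ²(1 − ρ).
- ANCOVA residual variance: σ²(1 − ρ²).
- Ratio k = (1 − ρ²)/[2(1 − ρ)] = (1 + ρ)/2.
- Power = Φ(0.39 × √(52/(2k)) − 1.96), with 0.39 in SDs of change and k = 1 for the change score.

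Change score: 0.39 × √26 = 1.989; Φ(0.029) = 51%.

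| ρ (assumed) | k | 1.989/√k | ANCOVA power | Gain (points) |
|---|---|---|---|---|
| 0.3 | 0.65 | 2.467 | 69% | 18 |
| 0.5 | 0.75 | 2.296 | 63% | 12 |
| 0.7 | 0.85 | 2.157 | 58% | 7 |
| 0.8 | 0.90 | 2.096 | 55% | 4 |

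SDs of change is the natural reading, because section 2c attaches 0.39 to a test of changes. If it were in SDs of the score (k = 2(1 − ρ) for change, 1 − ρ² for ANCOVA), power would go from 39 / 51 / 73 / 88% to 55 / 63 / 80 / 91%. The gains are similar; the levels are not.

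**3. What the SAP model does.** With two time points, complete data and unconstrained means, the arm-by-time contrast is the difference in mean change, so it gives the change-score result. With a common enrolment mean it has about the ANCOVA efficiency. The SAP does not say which applies.

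**4. Hospitalisation.** SAP inputs: 75% vs 50%, two-sided 5%, 52 per arm. The SAP states no power. Pooled proportion 0.625; null SE = √(0.625 × 0.375 × 2/52) = 0.0949; alternative SE = √((0.1875 + 0.25)/52) = 0.0917. Power = Φ((0.25 − 1.96 × 0.0949)/0.0917) = Φ(0.697) = 75.7%. With 58 per arm, the number the Protocol plans to randomise, it is 80.2%.

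The chi-square test was then compared with the Cochran-Mantel-Haenszel (CMH) test, without continuity correction, by simulation: 400,000 trials per scenario, two equal classes and overall rates fixed at 75% and 50%. The effect was either a constant 25-point difference or a common odds ratio. Class risks are assumed.

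| Class risk gap | Power change, 52 per arm | Power change, 58 per arm | False-positive rate at 52: chi-square / CMH |
|---|---|---|---|
| 0 | -0.4 | +0.1 | 5.2% / 5.0% |
| 10 points | -0.2 to -0.1 | +0.4 to +0.6 | not tabulated |
| 20 points | +0.4 to +0.8 | +1.7 to +2.3 | 4.6% / 5.0% |
| 30 points | +2.0 to +3.5 | +3.7 to +4.8 | 3.9% / 4.9% |

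With six strata (three classes by gender, about 8 to 9 patients per cell per arm; 200,000 trials), the CMH change was -1.2, -0.6 and +0.4 points for gaps of 0, 10 and 20 points.

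**The case against.** **The unadjusted chi-square is an accepted, valid choice.** This stands. A reader might infer that ignoring the stratum biases the comparison or inflates false positives. Among randomised patients it does not: the rate stays near or below 5%. Stratifying gains little at 52 per arm unless the class gap is near 30 points, and loses slightly if class is not prognostic.

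**Heart class is not ignored.** This also stands. The planned secondary inpatient analyses include heart class and gender. For ER, the natural reading of the covariate sentence in 2b is a secondary analysis too, since ER methods are described as similar to the inpatient ones. What remains is that no adjusted model is named for ER or QoL.

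**The SAP's mixed model may already solve the QoL problem.** It may. The loss is certain only for the Protocol's z-test; for the SAP it is an unstated model detail. The size also rests on an assumed correlation. At 0.8 the gain is about 4 points, which overlaps the larger stratification gains, so the order of the two points is not guaranteed.

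**Month 1 may simply mean the baseline visit.** The documents lean that way in places. PHQ4 is placed at month 1 in Table 1 and the TSM text, but at baseline in the control-group text and the confounder section. Table 1 also gives NYHA score at months 1 and 3, although class is checked before consent. One cannot conclude that the reference score is post-randomisation, only that the passages disagree.

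**Conclusion.** The point holds as a matter of efficiency and specification, not validity.

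- **QoL (main).** Conditioning on enrolment would add about 18 to 4 power points at 0.39 SD of change for correlations of 0.3 to 0.8, with 52 per arm and equal SDs. The gain applies to the Protocol's z-test taken as change from enrolment, and to the SAP model only if its enrolment means are unconstrained.
- **Hospitalisation and ER (minor).** The power change is about -0.4 to +0.8 points at 52 per arm for class gaps up to 20 points, and +2.0 to +3.5 at 30 points. The prognostic strength and shares of the classes are assumed.

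Protocol, Recruitment Procedures, also says that "enrollment for the telehealth arm of the study has ended and he/she will be enrolled in the standard of care arm". A reader might infer that non-randomised controls enter the primary comparison. The documents do not support that: the SAP limits the intention-to-treat set to randomised subjects. The number of such patients is not given, and the matter is separate from this point. Leaving them out has a price if they are counted in the 52. If 10 of 52 controls (assumed) were removed, pooled proportion 0.612, null SE 0.1011 and alternative SE 0.0963 give Φ(0.538) = 70.5% power, against 75.7%.

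**What to change.** **QoL**
1. Reconcile the reference score (enrolment or month 1) across Table 1, the two arm descriptions, section 2c and the SAP. Confirm that it was collected in both arms.
2. Analyse month 3 QoL by ANCOVA on arm, enrolment score and heart class, or by a mixed model with a common enrolment mean.
3. Do not subtract or condition on a score taken after randomisation.

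**Hospitalisation and ER**
1. Settle which factors were used in randomisation: heart class (SAP), or gender and Heart Class 3 (Protocol).
2. Use a CMH test and a stratified risk difference by that stratum for the yes/no outcomes, and add it to the count and length-of-stay models. Say that this is the primary analysis for ER as well, so that the covariate sentence in 2b has a defined place.
3. Keep the unadjusted tests as supportive.

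**Cost.** SAP wording and short code changes, with no new data if the enrolment score exists in both arms. The SAP implies that it does, but the control-group text gives months 1 and 3. The downside is up to about half a power point if heart class is not prognostic, and more (about 1.2 points in the six-stratum check) if gender is added and strata become sparse. The changes belong before unblinded analysis. The SAP is written in the past tense, so if results are already known, report these as labelled sensitivity analyses and leave the primary tests in place.

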Although many telehealth trials in community-dwelling seniors have been published, there is limited literature on the use of telehealth in *underserved populations*. The few telehealth studies conducted in disparity populations have focused primarily on diabetes and blood pressure management. Given the great discrepancy in prevalence rates of CVD disease and its manifestations between whites and ethnic minorities, coupled with the disparities in access to innovative and effective treatments between upper/middle and lower socioeconomic classes, it

is imperative that researchers and clinicians bring effective interventions to these at-risk populations.

The previous work of our research team includes a two-year randomized trial, a two-year matched control study, and a three-year randomized trial (currently underway). We have shown that TSM can create cost savings and shorter lengths of stay for those hospitalized. The present study proposes to test this technology with an underserved population to determine whether our previous results are generalizable.²⁶

OBJECTIVE(S)/SPECIFIC AIMS AND HYPOTHESES

Research Question: Can we narrow health disparities through TSM by providing the proposed disparity population with skills to monitor their health status daily and weekly access to a health practitioner through a scheduled telehealth video visit? We hypothesize that TSM patients will have significantly better outcomes: greater QoL and lower hospital utilization over 3 months than those receiving usual care.

In this study, we will apply appropriate and rigorous research methods to: *a*) assess patient acceptance and usability using a mixed methods approach; and *b*) directly compare TSM to standard of care in a health disparity population.

Aim 1: we will conduct a process evaluation to assess telehealth acceptance and usability among low-income, largely minority seniors living with CHF NYHA class 1-3.

We will use a mixed methods approach to look at indicators of usability, including qualitative measures, such as: 1) focus group feedback from key community stakeholders, including patients and caregivers, and quantitative measures, such as 1) rate of study participation acceptance; 2) self-monitoring behavior (as measured by vital sign uploads); 3) visit participation; 4) patient satisfaction; and 5) ease of use of measures.

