Aim 2:, we will conduct the first randomized controlled trial (RCT) to telemonitor minority community-dwelling patients with CHF (NYHA class1-3) for 3 months after hospital discharge for CHF. We will compare hospital and emergency room utilization, as well as QoL, between TSM and standard of care groups.

According to the NYHA classification system, patients experience increased limitations in physical activity, such as fatigue, palpitation and angina pain, from mild in class 1 to extreme in class 4. Patients in class 4 experience these symptoms even at rest, and are usually bedbound. We specifically excluded seniors with heart failure NYHA class 4 because they are primarily bed-bound and highly unlikely to be able to participate in the tasks required of the intervention.

Specifically, after hospitalization for a CHF exacerbation at NUMC, patients will be approached by the heart failure clinic nurse to assess interest in participation. The study will be described in detail, and patients will be assured of confidentiality. Once patients give permission, the clinic nurse will personally introduce the patient to the research nurse, and reiterate their willingness to participate, the formal consent process will occur. Patients will be randomized once they have given consent to participate in the study.

EXPERIMENTAL DESIGN

Aim 1: we will conduct a process evaluation to assess telehealth acceptance and usability among low-income, largely minority seniors living with CHF NYHA class 1-3.

We will assess usability of an existing Heart Failure telehealth intervention and will adapt the intervention to facilitate acceptability and feasibility in a population of low-income ethnic minority patients. Usability will be assessed throughout the study period through the examination of usability indicators presented temporally below.

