Meaures	TSM	SOC
Quality of Life Living with HF Questionnaire		
(Months 1 and 3)	x	x
NYHA Functional Score (Months 1 and 3)	x	x
Telemedicine Satisfaction and Usefulness		
Questionnaire (Month 3)	x	
PHQ4 to assess symptoms of depression		
and generalized anxiety disorder (Month 1)	,	×
DAILY ELECTRONIC TRANSMISSION OF		^
Blood Pressure	x	
Pulse	x	
Oxygen Saturation	x	
Weight	x	
WEEKLY VISIT	Video	Phone
Blood Pressure	х	
Pulse	x	
Oxygen Saturation	x	
Weight	x	
ER Utilization (Primary Outcome Variable)	x	x
Hospitalizations (Primary Outcome		
Variable)	x	x
Receipt of IV Diuretic	x	
Adherence with Diet Recommendations	x	
Dyspnea	x	
Fatigue	x	
Edema	x	
Death	x	x

Patients with CHF will be subjected to either TSM or standard of care as follow:

TSM Intervention. TSM is defined as a weekly visit and self-monitoring of daily vital signs utilizing a Subject Monitor which connects from the subject's residence, via a standard telephone line to the provider station (American TeleCare® Provider Station available in both English and Spanish language).

[figure not shown]
TSM has two components:

1) a daily vital signs self-monitoring component (client-side operation), which requires the subject to monitor and transmit standard key indicators of possible condition exacerbation to the server including blood pressure, oxygen saturation, weight, and pulse/heart rate, and

2) **a weekly telehealth visit**, wherein patients are instructed to attend a regularly scheduled video visit with

the practitioner (real time), and queried regarding their behavior and condition during that week.

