TSM Intervention Component 2: Telehealth Visit. Once a week, patients will be instructed to connect to the patient station for a weekly scheduled video telehealth (TSM) visit with the telehealth nurse. The video visit allows the subject and the provider to view one another and listen to the patient's heart and lung sounds. During the telehealth video visit, the patient and provider will discuss signs and symptoms of CHF and the practitioner will review the weekly uploads. Table 1 presents the indicators that will be obtained through the weekly visit for TSM and control patients in detail. For example, if the patient reports edema, further questioning will clarify the location and degree of the swelling and a treatment plan will be initiated. The

telehealth nurse will also ask the patient to show the area where edema is occurring on the monitor using the video camera on the telehealth machine. In addition, the provider will initiate a discussion regarding the importance of fluid and sodium management (see Table 2 for patient education management). In addition to these two components, QoL will be assessed at enrollment (immediately post-consent) and three months after enrollment utilizing the Minnesota Living with Heart Failure Questionnaire (QOL). Patients will also be assessed for symptoms of depression and generalized anxiety disorder using the PHQ4 questionnaire¹⁹ (Month 1; see appendix 5).

Standard of care (Control Group). Patients in the control group will receive usual care at NUMC Heart Failure clinic (primary and cardiac care as reimbursed by Medicare or sliding scale/uncompensated care). As noted above, usual care patients will be contacted on a weekly basis in order to maintain comparable frequency of contact. As detailed in Table 1, patients will be queried regarding ER, hospital utilization (primary outcome variables). They will also be assessed, at months 1 and 3, for QoL and for symptoms of depression and generalized anxiety disorder using the PHQ4 questionnaire¹⁹ (Baseline; see appendix 5). Finally, at the end of the study (month 3), they will be asked if their home care agency supplied any type of telehealth intervention using the attached survey (Control group exit survey).

SCHEDULE OF EVENTS: The table below delineates the expected schedule of events. Major milestones include: patient recruitment, CAB meetings, CAB focus groups, patient focus group, and data analysis.

INCLUSION AND EXCLUSION CRITERIA Subject Selection

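### The reference time point for quality-of-life change is inconsistent: month 1 in protocol section 2c, Table 1 and the control text; enrolment under the TSM heading and, by inference, in the SAP

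*Protocol*

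**What the plan says.** The documents give two reference points for the same outcome.

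**Month 1.**
- Protocol section 2c: "Measures of QoL are defined as the 3 month QoL score minus the 1 month QOL score". A two-sample z-test then compares these changes between arms.
- Protocol Table 1: the row "Quality of Life Living with HF Questionnaire" is labelled months 1 and 3 and is marked for both arms.
- Protocol, Standard of care (Control Group): controls are assessed for QoL at months 1 and 3.

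**Enrolment.**
- Protocol, TSM Intervention Component 2: "QoL will be assessed at enrollment (immediately post-consent) and three months after enrollment". The sentence stands under the TSM heading but names no arm.
- SAP, repeated-measures paragraph: changes between enrolment and 90 days are compared between groups. The sentence names no outcome. The next one says that the MLHFQ physical and emotional subscales were also analysed this way, so QoL is very likely meant, but this is an inference.

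Two further statements bear on the point. On allocation, Aim 2 says: "Patients will be randomized once they have given consent to participate in the study". The hypothesis under Objectives expects "greater QoL and lower hospital utilization over 3 months than those receiving usual care".

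**The concern.** A change score needs one reference visit, and for a randomised comparison that visit should come before treatment can act. Allocation follows consent, so a score taken a month later is a post-randomisation measurement. Subtracting it discards whatever the intervention achieved in that month. The resulting contrast describes month 1 to month 3, not the period since randomisation.

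QoL is named in the study hypothesis and in Aim 2, so the choice affects a main conclusion of the trial. Two people working from these documents could schedule, or subtract, different scores and each cite the protocol in support.

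**Working it through.** **1. What each definition estimates.** Let D0, D1 and D3 be the TSM-minus-control differences in mean MLHFQ score at enrolment, month 1 and month 3.
- Month 3 minus enrolment estimates D3 − D0. Randomisation makes D0 zero in expectation, so this is D3.
- Month 3 minus month 1 estimates D3 − D1. If a share f of the month-3 effect is present at month 1, this is (1 − f) × D3.

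The two agree only if f = 0 or if Month 1 is the enrolment score.

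**2. What Month 1 means.** The other labels, side by side:

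| Measure | Place | Label for first assessment |
|---|---|---|
| PHQ-4 | Table 1: "and generalized anxiety disorder (Month 1" | Month 1 |
| PHQ-4 | Component 2 paragraph | Month 1 |
| PHQ-4 | Control paragraph | months 1 and 3, and Baseline, in one sentence |
| PHQ-4 | Adjusting for Confounders | baseline only |
| NYHA | Table 1: "NYHA Functional Score (Months 1 and 3" | Month 1 |
| NYHA | Inclusion criteria | known before entry, since class decides eligibility |

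These labels favour reading Month 1 as the first assessment. Against that, the control paragraph equates month 3 with the end of the study, and by the same convention Month 1 would be the end of the first month. No sentence in the available text settles it.

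**3. The protocol's own QoL figure.** Section 2c claims 80% power for an effect size of 0.39 with 52 per group. It gives no alpha, so I assume two-sided 0.05, which the SAP uses for hospitalisation.
- Detectable effect = (1.960 + 0.842) × √(2/52) = 0.549, not 0.39.
- Power for 0.39 at 52 per group is 51%.

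This mismatch is a separate matter. It is noted here because 0.39 cannot serve as an 80% power starting point.

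**4. Illustration of the literal reading.** Power = Φ(k − 1.96) + Φ(−k − 1.96), where k = d × (1 − f)/r × √(52/2). Here d is the effect in SDs of change from enrolment to month 3, and r is the SD of change from month 1 divided by the SD of change from enrolment. The documents give neither f nor r, so both are assumed.

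| d | r | f = 0 | f = 0.25 | f = 0.50 |
|---|---|---|---|---|
| 0.39 | 1 | 51% | 32% | 17% |
| 0.55 | 1 | 80% | 56% | 29% |
| 0.55 | 0.9 | – | 65% | 34% |
| 0.55 | 0.8 | – | 75% | 42% |

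For example, d = 0.55, f = 0.50 and r = 1 give k = 0.275 × 5.099 = 1.402 and power 29%. The loss disappears when r falls to 1 − f: with f = 0.50 and r = 0.5, power is back at 80%. The results run from a large loss to none, so they show the mechanism and do not estimate its size in this trial.

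**The case against.** The strongest reply is that this is a labelling slip which the SAP has already resolved. The PHQ-4 and NYHA entries point to Month 1 as the first assessment. The only explicit description of when the first QoL score is taken places it straight after consent. The SAP uses enrolment and 90 days in a repeated-measures model, so the z-test in 2c may never have been applied. Much of this stands. On that reading there is no lost effect, and the proposed definition is close to what the SAP already describes. It does not remove the conflict: 2c, Table 1 and the control text still say otherwise, and the SAP sentence does not name the MLHFQ.

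A reader might infer three stronger things that the documents do not support.
- **That the arms were measured at different times, leaving controls without a baseline.** The enrolment sentence names no arm, and Table 1 gives both arms the same QoL schedule. The same paragraph refers to that table for both arms: "Table 1 presents the indicators that will be obtained through the weekly visit for TSM and control patients in detail".
- **That 2c plainly fails to test the hypothesis.** In "greater QoL and lower hospital utilization over 3 months than those receiving usual care", the three-month period may qualify utilization only.
- **That Month 1 is defined nowhere.** The schedule of events announced in the protocol and the appendices are not in the text available to me. I can say only that the available text does not define it.

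**Conclusion.** The inconsistency is certain from the text and should be corrected before any QoL result is reported. Its consequence is conditional. If Month 1 means the first assessment, the fault is a wrong label and nothing is lost. If 2c is followed literally, the reference score is post-randomisation, first-month benefit is removed, and the conclusion covers only month 1 to month 3. A particular drop in power should not be quoted as a finding, because the early share of effect and the SD ratio are both unknown.

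The QoL definition does not enter the utilization outcomes. I would not extend that into a blanket assurance about PHQ-4 timing. Section 2a leaves its primary analyses unadjusted, but section 2b says that ER utilization will be adjusted for potential confounders, and PHQ-4 symptoms are among those listed.

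**What to change.** 1. Define QoL change in both arms as the 90-day MLHFQ score minus the enrolment score, taken after consent and before the intervention starts.
2. Align section 2c, Table 1, the TSM and control paragraphs and the SAP repeated-measures sentence with this, and name the MLHFQ in that SAP sentence.
3. If Month 1 meant the first assessment, replace it with enrolment throughout, including the NYHA and PHQ-4 rows. The cost is wording only.
4. If first scores were in fact taken at one month in either arm, do not move the visit now. Recruitment Procedures says that telehealth-arm enrolment has ended and new patients enter standard of care, so a change would alter timing for later controls only and create a difference between arms. Report instead when the first score was taken in each arm, and limit the QoL conclusion to the month 1 to month 3 window. The SAP is written in the past tense, so this may be the only option left. Its cost is a narrower claim.

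As a separate minor point, reconcile the PHQ-4 schedule. Table 1 and the TSM text list Month 1 only, the control text months 1 and 3, and the confounder section baseline only. The SAP's repeated-measures and GEE analyses need a second assessment in both arms.
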